2.2. Total amount for entire participation. **\$160 over the 2 year study.**

3. Explain how compensation will be provided via cash, voucher, gift card, etc. **The subjects will receive a VA voucher that can be redeemed at the Cashier for cash.**
4. If financial compensation will be prorated, explain the process. **N/A**
5. Not Applicable -

T. Withdrawal/Early Withdrawal

1. Describe how and when a subject may withdrawal from the study. **Subjects may withdraw from the study at any time without consequences by contacting the PI in writing. Subjects may also inform any research staff member of their desire to discontinue their participation in the research study at any time. Staff members will then inform [name].**
2. Provide procedures for the orderly termination of participation by the participant and if any consequences would result from early withdrawal from the study. **Subjects may withdraw from the study at any time without consequences. Subjects who terminate from study treatment, but who are willing to remain active in the assessment portion of the research, will be followed by phone and encouraged to attend assessment visits at 6-months, 12-months, and 18-months after treatment groups begin, and check-ins at 3-, 6-, 9-, 12-, 15-, and 18-months after treatment groups begin. They will be referred back to their treatment team who will have been following them during their participation and kept informed of any study related matters.**
3. Explain if survival data is required. If so, clarify how data will be obtained. **Not Applicable.**
4. Not Applicable; subjects not recruited; chart review.

U. Risk/Benefit Assessment

1. Potential Study Risks

- 1.1. Describe and assess all of the following risks that may be associated with the research:
 - 1.1.1. **Physical – Assessment procedures at baseline are expected to take approximately 4-5 hours, while follow-up assessment sessions are expected to take approximately 3-4 hours. Check-ins will take approximately 15-minutes. Therapy sessions will take approximately 1 hour. Subjects may become uncomfortable during periods of prolonged sitting, and will be encouraged to requests breaks whenever necessary. Research staff will frequently check-in with subjects to determine if a break is necessary, and will be encouraged to supply breaks if they feel this is in the best interest of the subject.**
 - 1.1.2. **Psychological - Subjects may experience anxiety while completing the assessments or during iCBT sessions. They may feel uncomfortable answering questions, and may refuse any such questions. They may also feel tired or frustrated during the computerized training. They may be frustrated or stressed by the demands of looking for and maintaining employment in the SE setting. Subjects may become frustrated or angry with each other in the group setting.**
 - 1.1.3. **Social - NA**
 - 1.1.4. **Economic -NA**
 - 1.1.5. **Monetary - NA**
 - 1.1.6. **Legal - NA**
 - 1.1.7. **Loss of confidentiality There is a risk for breaches of confidentiality, especially in the setting of group treatment. All efforts will be taken to**

minimize this risk (i.e., secure storage of research documents, reviewing confidentiality in the therapy groups).

- 1.1.8. Assess the likelihood and seriousness of such risks. – **The likelihood of physical and psychological risks occurring is high, however the seriousness of these risks is considered minimal. The likelihood of a loss of confidentiality is moderate (given the group therapy session); the seriousness of this risk is considered moderate.**
- 1.1.9. Other– There may be other unforeseen risks. Subjects and the IRB will be notified in a timely manner if additional risks are discovered.
- 1.2. Specify what steps will be taken to minimize these risks. **Subjects will be counseled by their supported employment specialist/therapist if they are experiencing stress or agitation. They will be allowed to leave a group at any time if they feel it is necessary. As is part of the supported employment program, employment specialists will advocate for subjects with the employer should the subject be experiencing extra stress. This will be routinely done as part of the supported employment paradigm and not because the subject is involved in a research trial. If a subject becomes severely agitated, he or she will be brought to the emergency room for psychiatric evaluation by study staff and VA police.**
- 1.3. If methods of research create potential risks, describe other methods, if any, that were considered and why they will not be used. **Group interventions incur more risks than individual interventions, such as breaches of confidentiality and friction between group members. However, the benefits of a group approach to CBT and cognitive remediation outweigh the risks. The benefits relate to the additional learning subjects do in the group setting.**
- 1.4. If chart review, breach of confidentiality is always a concern. Specify what steps will be taken to minimize these risks. **Not Applicable.**

2. **Potential Study Benefits**

- 2.1. Assess the potential benefits to be gained by the individual subject, as well as benefits that may accrue to society in general as a result of the planned work. **Although antipsychotic medications have been readily available for more than half a century, the impact of these agents on functional outcomes has been modest, even when medication regimes have been optimized. By contrast, psychiatric rehabilitation programs have been shown to improve psychosocial functioning. Vocational rehabilitation services, in particular supported employment (SE), have the best evidence base. As compared to those patients not participating in such services, subjects successfully engaged in SE are more likely to be working competitive jobs, working full time, earning higher wages, and reporting a higher quality of life. Furthermore, steady employment has been shown to generate significant savings in the use of mental health services use compared to subjects who are minimally employed.**
- 2.2. If the subject does not receive any direct benefit, then it must be stated here and in the consent form. **Not Applicable.**

3. **Alternate Procedures**

- 3.1. Describe the alternatives available to the subject outside the research context. **The alternative for subjects is not to participate in the study and to continue treatment as usual with their clinical team receiving medications, supported employment, and therapy as prescribed routinely.**
- 3.2. If none, state that the alternative is not to take part in this research study at all. **Not Applicable.**

V. Data and Safety Monitoring Board (DSMB) or Data Monitoring Committee (DMC) (All Phase III studies are required to have a DSMB. However, the IRB has the right to require a DSMB with any study.)

1. **Will an independent DSMB or DMC oversee the project?** YES NO N/A
 - 1.1. If yes, please provide contact information for the DSMB or DMC or Coordinating Center Representative and attach a copy of the charter.
Name: _____ Phone Number: _____
Title: _____ E-mail: _____
2. **If a DSMB or DMC will not monitor this study, who will monitor this study? Check all that apply.**
 Principal Investigator
 Sponsor
 VA Cooperative Studies Program
 Safety monitoring committee

W. Data Monitoring (*Monitoring plans describe how a monitor, independent of the study team, regularly inspects study records to ensure the study is adhering to the study protocol and applicable research regulations and CMCVAMC requirements. Monitoring plans do not necessarily require the use of an independent Data and Safety Monitoring Board (DSMB). Such independent boards are usually reserved for high-risk phase I studies, or large, multi-center phase III trials. Federally funded studies may require the use of an independent DSMB.*)

1. **Describe the data monitoring plan** (All protocols must have a data monitoring plan appropriate for the potential risks and the complexity of the study.) **The PI and the rest of the study team will perform regular data monitoring to inspect study records to ensure the study is adhering to the study protocol and applicable research regulations and CMCVAMC requirements. This data monitoring will occur monthly and be overseen by the PI.**
2. **Describe how protocol deviations, adverse events, serious adverse events, breaches of confidentiality, unanticipated adverse device effect (UADE), and unanticipated or unexpected problems will be reported to the CMCVAMC IRB and sponsor** (*Refer to the CMCVAMC IRB Standard Operating Procedure (SOP) Manual for reporting guidelines.*)
Protocol deviations, serious adverse events, unanticipated or unexpected problems and breaches of confidentiality will be reported to the CMCVAMC IRB via email using the appropriate CMCVAMC forms in a timely manner (no more than 5 days) after learning of the event. Adverse events that are not considered serious will be reported to the IRB at the time of continuing review.
 - 2.1. Describe the management of information obtained that might be relevant to participant protections such as:
 - 2.1.1. Unanticipated problems involving risks to subjects or others: **We will update the informed consent form and make existing subjects aware of the new information through a revised informed consent procedure.**
 - 2.1.2. Interim results: **We will update the informed consent form and make existing subjects aware of the new information through a revised informed consent procedure.**
 - 2.1.3. Protocol modifications: **We will update the informed consent form and make existing subjects aware of the new information through a revised informed consent procedure.**
3. **If applicable, define the plan for subjects if research shows results such as:**
 - 3.1. Unanticipated problems involving risks to subjects or others – **Subjects and the IRB will be informed in a timely manner (as above) should any unanticipated risks to subjects be identified.**
 - 3.2. Interim results- **The IRB will be notified of interim results at the time of continuing review.**
 - 3.3. Protocol modifications **The IRB will be notified of requests for protocol modification prior to the institution of any modified procedures, either at the time of continuing review or in a stand-alone amendment request. Subjects will be notified in a**

timely manner about any protocol modifications that have a direct impact on research subjects (e.g., changes to consent form). If necessary, informed consent will be re-obtained.

To ensure the safety of participants, review of all collected information in the form of surveys and interview data will be conducted by study staff. If any current evidence of major depression, suicidal ideation, or homicidal ideation with no intent is present, this information will be discussed with the participant by a psychiatrist or doctoral level psychologist. The information will be provided to their mental health care provider for follow-up. In the case that a subject does not have a mental health care provider (e.g., they have left care against advice and/or after enrollment in the research study) they will be referred appropriately for treatment. If indicated, assistance will be provided in making this contact. If suicidal ideation or homicidal ideation with intent is present or there are reports of abuse of a child or elder, the participant will be referred for evaluation in the nearest emergency room and the treating mental health care provider will be notified. In emergent situations, emergency assistance will be sought from hospital security and/or by contacting 911 emergency services. Subjects may be withdrawn from the study if they are considered a risk to themselves or others. Subjects may continue with the study if they are psychologically stable, even if they do not have a current treating psychiatrist. However, they will be encouraged to reestablish clinical care.

4. Statistical Analysis

- 4.1. Include statistical power calculations and the assumptions made in making these calculations.

Power analysis

For the primary outcome variable (composite index of workforce participation), and secondary outcome, Work Behavior Inventory (WBI), we used an uncorrected alpha level (Type 1 error rate) of 0.05 in designing our study. There are many different perspectives on adjusting for multiple comparisons in general, and randomized trials in particular. A number of researchers believe that with a primary outcome and all other outcomes treated as secondary (i.e., exploratory) there is no need for multiple comparisons.

This study is powered to detect a clinically significant difference between iCBT and the usual care conditions. Meta-analysis of medical and behavioral outcomes indicates that a medium effect-size between conditions will have a significant impact on quality of life. In a previous study we observed an average effect of about $d=0.55$ SD. To allow for a somewhat smaller effect in this proposed study, we design our study to have 80% power to detect clinically significant effect of $d=0.5$ SD. In the pilot data, we found a within-subject correlation structure consistent with a stationary autoregressive process with correlation parameter 0.4. We also assume a dropout rate of 20% for these power calculations. With these assumptions on effect size, covariance structure, and dropout rates, and with a two-sided alpha level of 0.05, the methods of Hedeker et al.⁸⁶ estimate that a sample size of 48 subjects per group will provide 80% power for the test of our primary hypothesis.

We believe that this is a conservative estimate, based on the larger effect size observed in our prior study, and the higher than expected dropout rate used in the calculation. In addition, our analyses will use the baseline measure of Psychosocial Functioning as a covariate, which should reduce the standard errors in our test, and therefore increase the smallest detectable effect size.

4.2. Define plans for data and statistical analysis, including key elements of the statistical plan, stopping rules and endpoints.

Planned Analyses

(i) Overview

Logistic, log-linear and linear random effects models (hierarchical regression models) will be implemented with random intercepts and slopes for longitudinal binary, count, and continuous outcomes, respectively. These models will contain separate main effects for change from baseline to each follow-up visit at 6, 12, and 18 months, main effect for the treatment, and interactions between the visit and treatment indicator variables. For each of the primary (workforce participation indices) and the secondary (Work Behavior Inventory, Specific Levels of Function) outcomes, separate intent-to-treat (ITT) tests and estimates (with 95% confidence intervals) of randomized group contrasts at 6, 12, and 18 months will be obtained from the estimates of the respective time-treatment interactions.

We will assess residuals in the longitudinal linear random effects model with normal QQ plots and estimation of the skewness and kurtosis coefficients. If these are coefficients exceed their classical cut-offs of 3 and the QQ plots confirm skewness and/or kurtosis, we will then perform a longitudinal analysis based on a random effects generalized linear model with a gamma error distribution (with SAS Proc GLIMMIX) that handles skewed and kurtotic distributions. We will fit such a model with identity link function (linear mean model), such that the resulting estimates and tests are comparable to those of the normal error random effects model. We will compare the estimates and p-values. If the two approaches agree with respect to significance at the specified alpha level, then we will use the results from the linear random effects model with normal error. If they disagree we will base results on the gamma error distribution model.

Prior to each hierarchical analysis, baseline outcomes, pre-treatment assessment scores, and demographics (except gender which by definition is balanced due to be a stratification factor in the randomization) will be compared between the two treatments at the two-sided alpha = .05 level. Any significant baseline variables will be included as covariates in the hierarchical regression models. We will also perform as a sensitivity analysis based on an adjustment of the ITT models for post-randomization confounding due to differences in medication patterns between the randomized groups. Such adjustments will be based on a causal modeling approach that distinguishes between direct effects of the iCBT intervention, on the one hand, and differences in medication patterns, on the other, using randomization and its products with baseline covariates as the instrumental variables to control for unmeasured confounding due to choice of medication.

While the present study is designed to minimize lost observations, the proposed random effects or hierarchical regression approach is superior to last observation carried forward in minimizing bias and Type 1 error and inferentially equivalent to multiple imputation.⁷⁹ To assess the sensitivity of treatment effect estimates to missing data, we will compare the results under the above hierarchical regression models with those based on shared parameter models that account for informative missingness that is dependent on unobserved outcomes through a latent variable.⁸⁰ If the results between the two approaches are similar then we will present the proposed hierarchical regression models as robust to informative missing data; otherwise we will note that the results may be

sensitive to informative missing data and augment them with those based on the shared parameter model.

(ii) **Work outcome.** The primary trial outcome measure, workforce participation (composite index) at 6, 12 and 18 months analyzed in the manner described above. A significant ITT difference on the total WBI score across 6 and 12 months would support the hypothesis that iCBT is more efficacious than usual care at improving work outcomes by the end of treatment (Primary Aim 1). Similarly, WBI score at 18 months is a secondary outcome, and a separate ITT effect on work outcomes at 18 months with the respective month-treatment interaction in favor of iCBT would support the hypothesis that it promotes better work outcomes than usual care during the 6 months after the completion of treatment (Secondary Aim 2).

(iii) **Functional outcome.** The second trial outcome measures include the Work Behavior Inventory and the total score on the Specific Levels of Functioning Inventory (SLOF) at 12 months A significant ITT difference on the WBI and the total SLOF score across 6, 12 months would support the hypothesis that ICBT is more efficacious than usual care at improving functioning by the end of treatment (Secondary Aim 1). Similarly, WBI and SLOF total score at 18 months is a secondary outcome, and the separate ITT effects on functioning at 18 months with the respective month-treatment interaction in favor of iCBT would support the hypothesis that it promotes better functioning than usual care during the 6 months after the completion of treatment (Secondary Aim 3).

(iv) **Neurocognitive performance.** Following previously established procedures, accuracy scores of the neurocognitive domain scores most closely related to functioning (attention, verbal memory, and executive function) will be averaged to form the variable, neurocognitive performance (NP). The ITT analysis will be the same as for WBI. (Exploratory Aim 1).

(v) **Negative symptoms.** The sum of the 13 items of the Brief Negative Symptom Scale (BNSS) will serve as the index of negative symptoms. The ITT analysis will be the same as for work outcomes. (Exploratory Aim 2).

(vi) **Mediation and moderation.** We will follow the MacArthur model of identifying mediating and moderating variables by adding two terms to the above hierarchical regression models: main effects of the putative mediator on outcome, as well as interactive effects of the potential mediator by treatment condition (moderation) on outcome. With randomization and its products with baseline factors as instrumental variables, we also will test causally the effect of the intervention on outcome to see if there is full mediation (main effect of treatment is not significant) or partial mediation (main effect of treatment is still significant). Additionally, mediation analysis requires appropriate temporal ordering such that the mediator changes prior to the change in outcome that it putatively causes.⁸³ Four classes of model will be tested: (a) whether change in symptoms (mediators = SAPS total and BNSS total) mediates subsequent change in work outcomes or functional outcome (DVs = Workforce participation composite, WBI total, SLOF total) [Exploratory Aim 3], (b) whether change in neurocognition (mediator = composite score) mediates subsequent change in work outcome or psychosocial functioning (DVs = Workforce participation composite, WBI total, SLOF total) [Exploratory Aim 4], (c) whether change in dysfunctional attitudes (mediators = defeatist beliefs, asocial beliefs) mediates subsequent change in work outcomes and psychosocial functioning or symptoms (DVs = Workforce participation composite, WBI total, SLOF total)

[Exploratory Aim 5], (d) whether baseline prognostic variables predict treatment response independent of treatment condition and whether prescriptive factors predict differential treatment response (prognostic/moderator variables = illness duration, neurocognition, emotion recognition, cognitive insight, defeatist beliefs; DVs = Workforce participation composite, WBI total, SLOF total)
[Exploratory Aim 6].

X. Privacy and Confidentiality (*Privacy refers to persons and to their interest in controlling the access of others to themselves.*) (*Confidentiality refers to protecting information from unauthorized disclosure or intelligible interception.*) (*Investigator should contact the Privacy Officer for additional details.*)

1. Indicate the type of data that will be received by the Principal Investigator. Check all that apply.
 - 1.1. De-identified – Without any identifiers that could link the data to a specific participant. (Contact Privacy Officer for assistance. *If data is coded, it is not considered de-identified.*)
 - 1.2. Identified – Linked to a specific participant by identifiers sufficient to identify participants. (See [HIPAA](#) and [Common Rule](#) Criteria for list of identifiers.)
 - 1.3. Coded – Linked to a specific subject by a code rather than a direct identifier. If coded is checked, specify:
 - 1.3.1 Explain who will maintain the link or code. **The code key will be maintained by the principal investigator and research coordinator on a mapped network drive on a secure VA server (i.e., \\VHAPHIFPCMIRECC \Research Studies\[name] -Integrated CBT to Improve Work).**
 - 1.3.2 Describe who will have access to the link or code. **The study staff will have access to and maintain the code.**
 - 1.3.3 Provide exact details for how the data is coded. **Data will be coded by assigning subjects a study number based on consent order upon entrance into the study. The code will be kept separate from the rest of the data. In addition, when subjects who are in the CBT treatment arm are logged on to the Brain HQ server by their SES, they will be assigned a separate coded number, which will be maintained by the CMCVAMC study staff and not accessible by Posit Science at any time. CNB data are uploaded automatically to the VA MIRECC secure server using PGP encryption and reviewed for validity (i.e., \\VHAPHIFPCMIRECC \Research Studies\[name] -Integrated CBT to Improve Work).**
2. Does the project require the use of existing Protected Health Information (PHI) from a database, medical records, or research records? YES NO N/A
 - 2.1. If yes,
 - 2.1.1. Specify the source of the existing PHI **CPRS**
 - 2.1.2. Indicate the specific data elements/identifiers (e.g., name, address, phone numbers, etc.) on the below table.
 - 2.2. If the study uses an existing database/data warehouse,
 - 2.2.1. Provide a description of the database/data warehouse. **Not Applicable**
 - 2.2.2. Make clear who is responsible for maintaining it. **Not Applicable**
 - 2.2.3. Cite any relevant Standard Operating Procedures (SOP) for the database/data warehouse. **Not Applicable**
 - 2.2.4. Provide a copy of the SOP.
3. Will PHI be collected prior to obtaining informed consent? YES NO N/A
 - 3.1. If yes, complete and provide a HIPAA Waiver of Individual Authorization for Disclosure of Protected Health Information with this submission.
4. **HIPAA Identifiers** - Indicate the PHI that will be collected from project participants directly or indirectly.

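### The stated 80% power fits a difference in score levels, but the plan tests change from baseline, where power for 6 and 12 months combined runs from 58% to 87% depending on unstated baseline variance and dropout timing

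*Combined protocol and SAP*

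**What the plan says.** Section W.4.1 names the workforce-participation composite as primary and the WBI as secondary. Its inputs are d = 0.5 SD, a "within-subject correlation structure consistent with a stationary autoregressive process with correlation parameter 0.4", 20% dropout, two-sided alpha 0.05 and 48 per arm. From these, the cited methods "estimate that a sample size of 48 subjects per group will provide 80% power for the test of our primary hypothesis". It does not say which contrast or visits are meant, which SD scales d, or when dropout occurs. It adds that "our analyses will use the baseline measure of Psychosocial Functioning as a covariate". It describes this adjustment as a step "which should reduce the standard errors in our test, and therefore increase the smallest detectable effect size".

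Section W.4.2 (i) fits visit effects defined as change from baseline, a treatment main effect and their interactions. It plans "separate intent-to-treat (ITT) tests and estimates (with 95% confidence intervals) of randomized group contrasts at 6, 12, and 18 months", which "will be obtained from the estimates of the respective time-treatment interactions". Baseline variables are compared between arms at the two-sided .05 level, and "Any significant baseline variables will be included as covariates in the hierarchical regression models". Gender, the stratification factor, is exempt from that comparison and is nowhere put in the model.

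Section W.4.2 (ii) calls the composite at 6, 12 and 18 months the primary outcome, then judges Primary Aim 1 on the WBI total across 6 and 12 months. Section K lists several work indices over 18 months.

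**The concern.** With baseline as the reference visit, the treatment main effect is the arm difference at baseline. Each interaction is then the follow-up difference minus the baseline difference. Randomization makes the true baseline difference zero, so estimating and subtracting it can add noise without removing bias. Power for this contrast can therefore be well below power for a difference in levels, by an amount that depends on the baseline variance.

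At stake is what a null result would mean. If the 80% belongs to a different test from the one reported, a non-significant result may say less about a 0.5 SD effect than the plan implies. The covariate promised in W.4.1 might seem to repair this, but in the model as written it largely does not.

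**Working it through.** **Inputs from W.4.1:** d = 0.5, ρ = 0.4 with AR(1) decay, 48 per arm, 20% dropout, two-sided 0.05.

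**Assumptions, because the documents are silent:**
- d is in single-visit follow-up SD units and is the same at each follow-up visit.
- Baseline SD is s times follow-up SD, with s from 0 to 1.
- Retention at 6/12/18 months is gradual (.933/.867/.80), early (.80/.80/.80) or late (1/1/.80).
- The model is Gaussian. SEs come from generalized least squares, summing information over dropout patterns. Power = Φ(0.5/SE − 1.96).

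**Step 1: the plan's figure.** Take the difference in levels averaged over months 6 and 12. With complete data to month 12, the variance of a patient's mean is (1 + 1 + 2×0.4)/4 = 0.70. SE = √(2×0.70/48) = 0.171 and power is 83%. Gradual dropout gives SE 0.179 and 80%; early loss gives SE 0.191 and about 75%. The 80% is therefore reproduced under gradual dropout. It is not a unique fit: the 6+12+18 mean in levels with 20% lost at each visit gives 78%.

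**Step 2: the planned contrast.** The covariance of baseline with the 6+12 mean is s(0.4 + 0.16)/2 = 0.28s. The variance of the change is therefore 0.70 + s² − 0.56s. With complete data to month 12:
- s = 1: variance 1.14, SE = √(2×1.14/48) = 0.218, power 63%.
- s = 0.28 (the minimum): variance 0.622, SE 0.161, power 87%.
- s = 0: variance 0.70, power 83%.

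With all three dropout timings:

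| 6+12 contrast | Gradual | Early | Late |
|---|---|---|---|
| Planned, s = 1.0 | 61% | 58% | 63% |
| Planned, s = 0.75 | 73% | 69% | 76% |
| Planned, s = 0.5 | 82% | 77% | 85% |
| Planned, s = 0.25 | 84% | 79% | 87% |
| Planned, s = 0.1 | 82% | 78% | 86% |
| Planned, baseline near constant | 80% | 75% | 83% |
| Baseline-adjusted, or equal baseline means | 84% | 79% | 87% |

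The last row assumes that baseline varies. If it is constant there is nothing to adjust for, and the row above it applies. At s = 1 the effect detectable with 80% power, 2.80×SE, is 0.63 (gradual), 0.65 (early) or 0.61 (late), and 72–81 per arm would be needed.

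**Step 3: other windows.** The planned 6+12+18 contrast has 83–92% at s = 0.1–0.5 and 59–63% at s = 1. Planned single-visit tests have 39–61% at s = 1 and 53–76% at s = 0.1–0.5. With adjustment they have 59–76%.

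**Step 4: the covariate.** A baseline covariate entered as a main effect has one coefficient shared by all visits. It shifts the baseline and follow-up differences equally and drops out when one is subtracted from the other. With complete data and s = 1 the SE is 0.218 with or without it. With 20% dropout and a covariate correlation of 0.4, power moves only from 61.0% to 61.2% (gradual) or from 57.3% to 58.2% (early). At a correlation of 0.6 it reaches 61.9% and 59.9%. These last runs use whole-patient dropout counts, so they differ slightly from the table.

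**Step 5: direction.** The detectable effect is 2.80×SE, so a smaller SE lowers it. W.4.1 says that it rises.

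**The case against.** The strongest reply is that the low figures need an unlikely input. Participants are severely disabled, not using rehabilitation services and about to enter supported employment, and the WBI is scored zero when a patient is not working (section O.2.1.1). Baseline work scores may vary little, and then the planned 6+12 contrast has about 75–87%, around the stated 80%. For the composite over all three visits it exceeds 80% once baseline SD is half of follow-up or less. This stands as a plausible case. It is not established: the inclusion criteria do not require unemployment, and W.4.1's only statement on variance is the word stationary, which read literally means equal variances.

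Several stronger readings are tempting but unsupported:
- A reader might infer that the 80% is an arithmetic error. It is reproducible.
- A reader might infer that no outcome is named. W.4.1 names the composite and the WBI. What is missing is the contrast, the SD behind d and the dropout timing.
- A reader might blame the whole 58–87% spread on baseline variance. Part of it is dropout timing; the range at each timing is given separately above.
- A reader might infer that the single-visit tests break a promise. The documents claim 80% only for the primary hypothesis.
- A reader might see the fixed Psychosocial Functioning covariate and the significance screen as contradictory. The screen does not say that only significant variables enter, so the two can coexist. But the baseline of the work outcome itself enters as a covariate only through the screen, which chance alone triggers in about 5% of trials.

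The cited power method was not available and might fix some of these choices.

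**Conclusion.** The point holds as a mismatch and an under-specification. The 80% is right for a 6+12-month difference in levels under gradual dropout, but that is not the contrast described in W.4.2 (i). For the planned contrast the documents do not determine the power: it is 58–63% if baseline and follow-up variances are equal and about 75–87% if baseline variance is low. The single-visit tests stay below 80% in every case examined, so a null result at one visit would be weak evidence against 0.5 SD.

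In these calculations, adjusting for baseline never lowers power, and it removes the dependence on baseline variance except in the limit of a constant baseline. The figures are a Gaussian AR(1) approximation. The plan's random intercept-and-slope, logistic and log-linear models could differ, and the exact cancellation in Step 4 is shown only for the linear model with complete data.

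**What to change.** 1. Either keep baseline as a visit and constrain its mean to be equal across arms, or model only the follow-up visits and always include the baseline value of the outcome analysed. Adding that value as a main effect to the present model would gain little.
2. Always include gender, and replace the baseline significance screen in W.4.2 (i) with these prespecified covariates.
3. Reconcile W.4.2 (ii), where Primary Aim 1 is judged on the WBI at 6 and 12 months, with W.4.1 and section K, where the primary outcome is the composite or indices over 18 months. The outcome and window are the sponsor's choice.
4. Have the sponsor recompute power for that outcome and window, stating the contrast, the SD that scales d, the dropout timing and the baseline variance. Indicatively, the adjusted 6+12 contrast has 79–87%, or 75–83% if baseline is constant.
5. In W.4.1, change the statement that the detectable effect will increase to say that it will decrease.

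The cost is minor rewording and a revised power paragraph. Table 1 already collects the WBI and workforce participation at baseline, so no new data or patients are needed. The drawback is that the restated power may be slightly below 80%.
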